The Efficacy and Safety of Silodosin Singly or Combined with Ningmitai Capsules in the Treatment of Benign Prostatic Hyperplasia (BPH) Complicated with Lower Urinary Tract Symptoms (LUTS) —A Multicenter, Prospective, Randomized, Doubleblind, Positive Controlled Study

Date: September 8, 2022

Research Proposal Summary

Scheme number	NM-22-A-001-YJ-001					
Scheme name	The Efficacy and Safety of Silodosin Capsules Singly or Combined with Ningmitai Capsules in the Treatment of Benign Prostatic Hyperplasia					
Version number/date	Version 1.0, December2, 2021					
sponsor	Shanghai Haitian Pharmaceutical Technology Development Co., Ltd.					
Clinical trial staging	Post-marketing clinical re-evaluation					
test drug	Ningmitai Capsules (Ningmitai [®] , Z20025442), each 0.38g, was produced by Guiyang Xintian Pharmaceutical Co., Ltd.					
	Silodosin Capsules (Qianweitai®, H20213612), each 4mg, was produced by Shanghai Huilun Pharmaceutical Co., Ltd.					
	Tamsulosin Hydrochloride Sustained Release Capsules(H20000681), each0.2mg, was produced by Astellas Pharma Inc.					
	Placebo, Ningmitai capsule simulator, each0.38g, was produced by Guiyang Xintian Pharmaceutical Co., Ltd.					
Indications	Benign Prostatic Hyperplasia with Lower Urinary Tract Symptom					
Test purposes	1.To evaluate the efficacy and safety of Silodosin Capsules alone versus Tamsulosin Hydrochloride Sustained Release Capsules in the treatment of BPH with lower urinary tract symptoms.					
	2.To evaluate the efficacy and safety of Ningmitai Capsules combination with Silodosin Capsules versus Silodosin Capsules alone in the treatment of BPH with lower urinary tract symptoms.					
Research design	A multicenter, prospective, randomized, controlled clinical trial design					
total number	It is planned to complete 312 cases (considering the 20% dropout rate)					
number of research	8					

centers					
Study period	6 months				
research	Diagnostic criteria:				
object	1. Male Subjects aged 60 ~ 80 years, clinically diagnosed as benign prostatic hyperplasia.				
	2. Has an IPSS score ≥ 8 points at Screening and Baseline.				
	3. Has a $4 \le Q_{max} \le 15$ ml/s when urination volume > 150 ml.				
	4. Has a prostate volume (PV) \geq 30 ml by ultrasound examination.				
	5. Subjects who can read, understand, and complete the research questionnaire.				
	6. Subjects willing to participate voluntarily in this clinical trial, give informed consent and sign				
	informed consent.				

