The Efficacy and Safety of Silodosin Singly or Combined with Ningmitai Capsules in the Treatment of Benign Prostatic Hyperplasia (BPH) Complicated with Lower Urinary Tract Symptoms (LUTS) —A Multicenter, Prospective, Randomized, Double-blind, Positive Controlled Study

Date: September 8, 2022

Statistical analysis Plan

1.Statistical analysis of population:

- (1) **FAS:** According to the basic principle of intentionality analysis (ITT), all the randomized subjects with more than one medication record and effectiveness evaluation were included in the full analysis set. The total analysis set is the main validity evaluation population of this study.
- (2) **PPS:** Include all subjects who have completed the treatment stipulated in the scheme or have not seriously violated the trial scheme. The exact definition of the serious violation scheme will be finalized during the data review. PPS is the secondary analysis population of validity, but if its results are inconsistent with the full analysis set, it is necessary to analyze the inconsistent results in detail.
- (3) **SS:** Defined as all subjects who were randomized and received at least one trial drug treatment. The safety analysis set is the safety evaluation population of this study.

2.Statistical analysis method:

- (1) **General principle:** All statistical analysis shall be processed by SPSS 23.0 and above statistical software, and shall be carried out according to the pre-established statistical analysis plan. Measurement data are described by mean, standard deviation, median, quartile, maximum and minimum. The counting data are described by frequency and percentage. After 12 weeks of treatment, the changes of IPSS scores between Tamsulosin + placebo group and Silodosin + placebo group were compared by non-inferior test, while the changes of IPSS scores between Ningmitai + Silodosin group and Silodosin + placebo group were compared by superior test, and the test levels were $\alpha = 0.025$ (unilateral). Other hypotheses were tested by two-side test with a test level of $\alpha=0.05$, and the secondary index was adjusted by Bonferroni method with a test level of $\alpha=0.0167$.

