- (2) **Balance analysis of baseline value:** Comparability analysis of demographic characteristics, general situation and baseline situation (before treatment) of the two groups of data. Among them, t test or Wilcoxon rank sum test was used for measurement data and grade data, and χ^2 test or Fisher exact probability method was used for classification data.
- (3) **Effectiveness analysis:** Conducted in FAS and PPS at the same time.

① **Main endpoint indicators:** After 12 weeks of treatment, the difference of IPSS score decline and 97.5% CI of the three groups were calculated. If the lower limit of unilateral 97.5% confidence interval of the difference of IPSS score decline between Silodosin + placebo group and Tamsulosin + placebo group is greater than the non-inferiority threshold of 1 (-1 point), then "Silodosin + placebo" is not inferior to "Tamsulosin + placebo" group. If the lower limit of unilateral 97.5% confidence interval of the difference between the IPSS scores of Silodosin + Ningmitai group and Silodosin + placebo group is greater than the superior effect threshold of 2 (0 points), then "Silodosin + Ningmitai" is superior to "Silodosin +

placebo". Subgroup analysis was considered according to whether the NIH-CPSI pain score was ≥ 4 before treatment and the severity of IPSS total score.

②Secondary endpoint index: The changes of IPSS scores, IPSS sub-scores and QoL scores were compared between groups at 1, 2, 4, 8 and 12 weeks after treatment. The changes of Q_{max} , PVR, serum PSA and prostate volume were compared between groups by single factor analysis of variance or Wilcoxon rank sum test. Bonferroni method was used to adjust the test $\alpha = 0.0167$. The clinical progression curve of BPH was drawn by Kaplan-Meier; COX regression model was used to compare the factors affecting the clinical progression of BPH. The proportion of patients with IPSS total score decreased in severity was compared between groups by χ^2 test or Fisher exact probability method.

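### Neither primary IPSS comparison has a stated model; prespecifying ANCOVA on baseline IPSS would gain precision at almost no cost (an improvement, not an error)

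*SAP*

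**What the plan says.** The protocol's primary endpoint is the change in IPSS from baseline to week 12. SAP 2(1), General principle, assigns a non-inferiority test to silodosin versus tamsulosin; for the other contrast it says "while the changes of IPSS scores between Ningmitai + Silodosin group and Silodosin + placebo group were compared by superior test". Each is tested at one-sided alpha 0.025.

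SAP 2(3)①, Main endpoint indicators, says "After 12 weeks of treatment, the difference of IPSS score decline and 97.5% CI of the three groups were calculated". Non-inferiority is declared if the lower limit "is greater than the non-inferiority threshold of 1 (-1 point"), and superiority if it "is greater than the superior effect threshold of 2 (0 points"). No test statistic, regression model, covariate or centre term is given for either comparison.

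The secondary paragraph, 2(3)②, does not fill the gap. It says "The changes of IPSS scores, IPSS sub-scores and QoL scores were compared between groups" without naming a method. Its one-way ANOVA or rank test is attached to other outcomes: Qmax, then "PVR, serum PSA and prostate volume were compared between groups by single factor analysis of variance or Wilcoxon rank sum test".

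The SAP uses baseline values in two other ways only: for the comparability check in 2(2) and to define subgroups. Baseline IPSS is nevertheless available for everyone enrolled, because the protocol's entry criteria require it: "Has an IPSS score ≥ 8 points at Screening and Baseline".

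**The concern.** Both primary claims depend on where a lower confidence limit falls, so the width of the interval matters directly, above all against a margin of only 1 point. Taking an unadjusted difference in change scores amounts to fixing the slope of week-12 IPSS on baseline IPSS at 1. If the true slope is anything else, part of the outcome variance that baseline could explain stays in the error term and widens both intervals.

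There is a second, smaller issue. A plan that is silent on the model, but does schedule baseline comparability tests, does not say whether those tests could lead to adjustment. Naming the model and closing the covariate list removes that discretion from the result that decides both claims.

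**Working it through.** **Inputs from the documents.** 312 patients, 20% dropout, 1:1:1 allocation, one-sided alpha 0.025, thresholds -1 and 0. Patients per arm: 312/3 = 104; after 20% loss, 312 × 0.8/3 = 83.2, taken as 83. The documents give no SD, correlation, expected difference or power, so 312 cannot be reproduced and everything below rests on stated assumptions.

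**Variance comparison (needs no absolute SD).** Let s be the baseline SD, k the ratio of week-12 SD to baseline SD, and ρ the baseline to week-12 correlation. The slope is ρk.

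- Var(change) = s²(1 + k² − 2ρk)
- Var(ANCOVA) = s²k²(1 − ρ²)
- Difference = s²(1 − ρk)², which is zero only when the slope is 1
- Ratio = k²(1 − ρ²)/(1 + k² − 2ρk); for k = 1 this is (1 + ρ)/2

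| k | ρ = 0.3 | ρ = 0.5 | ρ = 0.7 |
|---|---|---|---|
| 0.8 | 0.502 | 0.571 | 0.628 |
| 1.0 | 0.650 | 0.750 | 0.850 |
| 1.3 | 0.805 | 0.912 | 0.991 |
| 1.5 | 0.871 | 0.964 | 0.998 |

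At k = 1 the interval narrows by 1 − √ratio = 19%, 13% and 8%. The equivalent unadjusted size is 83/ratio = 128, 111 and 98 per arm. Over k from 0.8 to 1.3 the extremes are 83/0.502 = 165 and 83/0.991 = 84.

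**Entry restriction.** A simulation with baseline IPSS cut to 8–35 (assumed mean 18 and SD 6 before the cut, equal SDs, 83 per arm) gave ratios of 0.70, 0.79 and 0.88 for ρ = 0.3, 0.5 and 0.7, so savings of about 30%, 21% and 12%.

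**Absolute effect on non-inferiority.** Half-width = 1.96 × SD × √(2/n). Power at true difference 0 = Φ(1/(SD√(2/n)) − 1.96). The adjusted SD is SD × √0.75 (k = 1, ρ = 0.5). SD here means the SD of change, and all three values are assumed. The value 2.3 is the SD that would give 80% power with 83 per arm: 1/((1.96 + 0.842) × √(2/83)) = 2.30.

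| n per arm | SD | Half-width, unadjusted → adjusted | Power, unadjusted → adjusted |
|---|---|---|---|
| 83 | 2.3 | 0.70 → 0.61 | 80% → 90% |
| 83 | 5 | 1.52 → 1.32 | 25% → 32% |
| 83 | 7 | 2.13 → 1.84 | 15% → 18% |
| 104 | 2.3 | 0.63 → 0.54 | 88% → 95% |
| 104 | 5 | 1.36 → 1.18 | 30% → 38% |
| 104 | 7 | 1.90 → 1.65 | 18% → 22% |

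The rows with 104 apply if 312 means completers. Over k from 0.8 to 1.3 and ρ from 0.3 to 0.7 at 83 per arm, power rises by 0.4 to 17.7 points (SD 2.3), 0.2 to 19.3 (SD 5) and 0.1 to 10.5 (SD 7).

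**Simulation check.** In 20,000 three-arm trials per SD (83 per arm, k = 1, ρ = 0.5), power went from 0.798 to 0.895, 0.246 to 0.313 and 0.150 to 0.183 for SD 2.3, 5 and 7. One-sided type I error at a true difference of -1 was 0.024 to 0.025 unadjusted and 0.023 to 0.027 adjusted.

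**The case against.** The strongest reply is that nothing here is wrong. The unadjusted comparison is unbiased over randomization and keeps its type I error, and the SAP does state the contrasts, alpha and decision rules. That stands, and it is why this is a recommendation only.

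The size of the benefit is also open. A range from 50% down to 1% includes almost nothing, and the most striking figure, 80% to 90% power, is the least realistic. A change SD of 2.3 would imply a baseline SD of only 1.7 to 3.2 over the same k and ρ range, which fits poorly with a population that the plan divides into IPSS 8–19 and 20–35. At SD 5 or 7, non-inferiority power at a true difference of 0 stays low with or without adjustment: ANCOVA does not make up for a sample size whose basis is undocumented. The entry cut-off also trims the k = 1 savings somewhat. All of this stands as a limit on the illustration.

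Finally, the calculations assume complete, normally distributed data, while the plan expects 20% dropout and says of the FAS that "The total analysis set is the main validity evaluation population of this study". The handling of missing week-12 scores will affect the interval too, but it has to be settled for either analysis. None of these points favours leaving the model unstated or leaving baseline out of it.

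**Conclusion.** The point holds as an improvement that should be made; the plan is not invalid without it. The SAP specifies no model for either primary comparison, and ANCOVA on baseline IPSS is more precise than the implied unadjusted analysis unless the true slope is 1. The reading as unadjusted is inferred from the wording. The central illustration is a 15% to 35% variance saving (equal SDs, ρ from 0.7 down to 0.3), within a wider range of about 1% to 50%. Where this trial falls in that range cannot be known from the documents. Confidence in the direction is high; the gain could be small if the slope is near 1.

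**What to change.** Before unblinding, add to SAP 2(3)①:

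- The primary analysis is ANCOVA of the week-12 IPSS decline on treatment arm (three levels), with baseline IPSS as a continuous covariate.
- State whether centre (8 planned) is in the model, and that no other covariates will be added.
- Compare the lower one-sided 97.5% limits of the adjusted contrasts, silodosin minus tamsulosin and combination minus silodosin, with -1 and 0. These equal the lower limits of two-sided 95% intervals. The thresholds carry over because, under randomization, the adjusted contrast estimates the same mean difference.
- Keep the unadjusted difference as a named sensitivity analysis.
- Apply the same rule for FAS participants without a week-12 IPSS to both analyses.

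The cost is a few sentences and a standard procedure in SPSS, which the SAP already names. No new data are needed, and alpha, margin and sample size stay as they are. In the worst case (slope exactly 1) the covariate costs about one error degree of freedom: 3 × 83 − 3 = 246 becomes 245. A centre term would use 7 more, which is negligible at this size.

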Course of treatment: 12 weeks

Visit points: screening period, days -28 to 0), after 1 week of treatment (day 7 ± 2), after 2 weeks of treatment (day 14 ± 3), after 4 weeks of treatment (day 28 ± 5), after 8 weeks of treatment (day 56 ± 7), after 12 weeks of treatment (day 84 ± 10).

Research steps

This trial is divided into two stages: screening period, treatment period and follow-up period.

Screening period (days -28 to 0): After signing the informed consent form, the subjects entered the screening period, and made a 24-hour urination diary and screening examination.

Treatment and Follow-up period: eligible patients were randomly assigned to three groups according to 1: 1: 1 and received Tamsulosin + placebo, Silodosin + placebo or Silodosin + Ningmitai for 12 weeks. During the treatment period, the subjects' diaries were recorded according to the requirements of the scheme, and they were followed up at 1 week (7 ± 2 days), 2 weeks (14 ± 3), 4 weeks (28 ± 5 days), 8 weeks (56 ± 7 days) and 12 weeks (84 ± 10 days). During the visit, relevant scale scores and laboratory examinations were performed, and the occurrence of adverse events during the follow-up was recorded to evaluate the safety.

study endpoint

Primary endpoint:

International Prostate Symptom Score (IPSS), Changes of scores at the 12th week of treatment compared to the baseline scores.

Secondary endpoints:

1.IPSS Score

- ①changes of IPSS total score: Changes of IPSS scores at 1, 2, 4 and 8 weeks after treatment compared with baseline scores
- ②Proportion of patients with IPSS total score severity decreased by at least one grade at 12 weeks
- ③IPSS sub-score: IPSS Stimulation Score at 1, 2, 4, 8, 12 weeks (Sum of Question 2, 4, 7) and

Changes of IPSS obstruction score (sum of question 1, 3, 5, 6) compared with baseline.

- 2.Quality of life (QoL) score: Changes in scores at 4, 8 and 12 weeks of treatment compared with baseline
- 3. Maximum urinary flow rate (Q_{max})

The change of Q_{max} at 12 weeks of treatment compared with baseline.

4. Patient response rate

Patient response rate is defined as the proportion of patients whose IPSS total score decreased by \geq 25% and Q_{max} .

increased by $\geq 30\%$ compared with baseline value after treatment.

5. Residual urine volume (PVR)

Changes of PVR at 12 weeks of treatment compared with baseline.

6. Prostate specific antigen (PSA)

Changes of PSA at 12 weeks of treatment compared with baseline.

7. Prostate volume (PV)

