
Changes of IPSS obstruction score (sum of question 1, 3, 5, 6) compared with baseline.
 
2. Quality of life (QoL) score: Changes in scores at 4, 8 and 12 weeks of treatment compared with baseline
 
3. Maximum urinary flow rate (Q_{max})
 
The change of Q_{max} at 12 weeks of treatment compared with baseline.
 
4. Patient response rate
 
Patient response rate is defined as the proportion of patients whose IPSS total score decreased by $\geq 25\%$ and Q_{max} increased by $\geq 30\%$ compared with baseline value after treatment.
 
5. Residual urine volume (PVR)
 
Changes of PVR at 12 weeks of treatment compared with baseline.
 
6. Prostate specific antigen (PSA)
 
Changes of PSA at 12 weeks of treatment compared with baseline.
 
7. Prostate volume (PV)
 
Changes of PV at 12 weeks of treatment compared with baseline.
 
8. Proportion of patients with BPH clinical progression
 
Clinical progress is defined as the first occurrence of one of the following two conditions during the trial:
 
 ① Acute urinary retention (AUR). ② Clinical diagnosis requires surgical treatment of BPH. 
Subgroup analysis:
 
Patients were grouped according to the following conditions of subjects at baseline, and the therapeutic effect of curative effect indicators was evaluated among different subgroups to determine whether the therapeutic effect was consistent among subgroups:
 
 ① The scores of IPSS were moderate (8-19) and severe (20-35); ② Routine examination of EPS (EPS leukocytes > 4HP or < 4HP. If EPS is not collected after prostate massage, it is not advisable to repeat massage for many times, and it is recommended to take urine after prostate massage for analysis.). ③ Symptoms of chronic prostatitis (NIH-CPSI pain score ≥ 4 and < 4)

security indicators	
The incidence of adverse drug events/reactions was calculated according to the following indicators:
 
1.Vital signs: Blood pressure, heart rate2.Laboratory examination index: Blood routine, Urine routine, liver function (ALT, AST, ALP) and renal function (BUN, Scr).3.Possible adverse drug events/reactions.
--------------------------------	--

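### Does the superiority rule for IPSS point the wrong way because it leaves out the word decline?

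*SAP*

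**What the plan says.** SAP section 2(3), under the main endpoint indicators, opens by saying that after 12 weeks "the difference of IPSS score decline and 97.5% CI of the three groups were calculated". Two decision rules follow.

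- **Non-inferiority.** The one-sided 97.5% lower limit for the difference in IPSS decline, with silodosin named before tamsulosin, must exceed −1 point.
- **Superiority.** The same kind of limit is required, but the quantity is worded as "the difference between the IPSS scores of Silodosin + Ningmitai group and Silodosin + placebo group is greater than" a threshold of 0 points. The word decline does not appear.

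SAP section 2(1) describes the second contrast in a third way: "the changes of IPSS scores between Ningmitai + Silodosin group and Silodosin + placebo group were compared by superior test". The protocol's primary endpoint is "Changes of scores at the 12th week of treatment compared to the baseline scores". Neither document writes change as a formula or says which group is subtracted from which.

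The direction of the scale is clear. The subgroup definitions place severe disease at 20 to 35, above moderate at 8 to 19, and the response endpoint begins "Patient response rate is defined as the proportion of patients whose IPSS total score decreased by", so a fall in score is the benefit.

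**The concern.** One primary contrast is described by three terms: scores, changes and decline. They do not share a sign. A larger decline is good. A larger score is bad, and so is a larger value of week 12 minus baseline. The superiority sentence uses the term with the unfavourable sign and yet requires the lower limit to exceed 0.

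If an analyst computed combination minus silodosin on scores, or on week 12 minus baseline, and applied that sentence by itself, a combination that significantly worsened symptoms would be declared superior, and one that significantly improved them would fail. The sentence decides the trial's second primary question, so an error there would reverse a headline conclusion.

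**Working it through.** **Step 1: which readings are possible.** Write B for silodosin + placebo and C for silodosin + Ningmitai. The rule is that the lower limit exceeds 0.

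| Quantity | C minus B | B minus C |
|---|---|---|
| Decline (baseline minus week 12) | C better: right way | C worse: wrong way |
| Score at week 12, or week 12 minus baseline | C worse: wrong way | C better: right way |

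The direction depends on two choices, the quantity and the order. The superiority sentence alone settles neither.

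**Step 2: what the paragraph settles.**

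- *Quantity.* The opening sentence names the difference in decline, for all three groups, as the estimate to be calculated with its interval. It is the only interval that the paragraph introduces, so both rules are rules for reading it. SAP section 2(1) and the protocol endpoint, although unsigned, both refer to change, so neither supports an analysis of raw week-12 scores.
- *Order.* The non-inferiority rule is stated on decline, with a lower limit above −1 and the conclusion that silodosin is not inferior. That holds only if the order is silodosin minus tamsulosin, the first-named group minus the second. The opposite order would show that tamsulosin is not inferior to silodosin. The superiority sentence has the same form and names the combination first, so its order is C minus B.

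Together these select the top-left cell, which is correctly directed and agrees with the rule's stated conclusion that the combination is superior.

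The bracketed values, −1 and 0 points, are taken as the operative thresholds. The bare digits printed before them may be labels whose symbol was lost in text extraction, and the direction does not depend on them.

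**Step 3: what a reversal would do.** The documents give 312 patients, three equal arms and 20% dropout: 312/3 = 104, and 104 × 0.8 = 83.2, taken as 83 per arm. They give no SD and no assumed effect, so SD 4 to 7 and a true difference of 2 points are assumptions.

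SE = SD × √(2/83)

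Correct rule, C better by 2: P = P(Z > 1.96 − 2/SE)

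Reversed rule, C worse by 2: P = P(Z > 1.96 − 2/SE), the same expression

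| SD | SE | Correct rule, C 2 better | Reversed rule, C 2 worse |
|---|---|---|---|
| 4 | 0.621 | 0.90 | 0.90 |
| 5 | 0.776 | 0.73 | 0.73 |
| 6 | 0.931 | 0.57 | 0.57 |
| 7 | 1.087 | 0.45 | 0.45 |

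At no true difference, both rules pass 0.025 of the time. Under the reversed rule, a combination that is truly 2 points better would pass with probability 0.0001 or less. The two probability columns are identical because reversing the rule only swaps which direction of effect it detects. They show how bad a reversal would be and say nothing about whether the text leads to one.

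**The case for a change.** The best case for a change is that a confirmatory rule should identify its variable, sign and order of subtraction without help from neighbouring sentences. This one does not. Week 12 minus baseline is a common coding of change, and the protocol endpoint does not exclude it. Read strictly, the sentence even departs from the endpoint, since scores at week 12 are not changes. The repair would cost one phrase.

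The omission stands, as does the absence of any written formula. The claim that the plan gives no direction does not stand: decline is a direction, and it is set in the sentence that opens the paragraph. Nor is the wrong-way reading simply the literal one. It takes the order of subtraction from the parallel non-inferiority sentence while discarding the quantity that the same sentence supplies. An analyst who did this would also have to report higher symptom scores as superiority, against the response definition and the severity bands. If the interval included 0, both versions would give the same answer, not superior. The low cost of an edit does not make it necessary, because the edit would alter no test, alpha, threshold or result.

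**Conclusion.** The concern does not call for a change. The superiority sentence omits a word that the sentences before it supply, and read with them the rule is correctly directed: decline on the combination minus decline on silodosin + placebo, lower limit above 0. Someone following the paragraph as written would reach the right verdict. This rests on treating the opening sentence as governing both rules, which is the natural reading because it introduces the only interval in the paragraph.

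The 57% to 90% range (SD 4 to 6, 83 per arm, 2-point difference, all but the patient numbers assumed) describes a misreading that the text does not invite. It should not be read as a risk of a false claim in this trial.

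### Changes in Qmax, PVR, PSA and prostate volume are compared without baseline as a covariate, and the pairwise procedure implied by the 0.0167 level is not named

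*SAP*

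**What the plan says.** For the changes in Qmax, PVR, PSA and prostate volume, SAP 2(3)② says they are "compared between groups by single factor analysis of variance or Wilcoxon rank sum test". No covariate is named. The next sentence reads "Bonferroni method was used to adjust the test" and gives the level 0.0167. SAP 2(1) agrees: "Other hypotheses were tested by two-side test with a test level of" 0.05, and "the secondary index was adjusted by Bonferroni method with a test level of" 0.0167.

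Both objectives in the Protocol (Test purposes) concern a pair of arms. The first is "To evaluate the efficacy and safety of Silodosin Capsules alone versus Tamsulosin Hydrochloride Sustained Release Capsules" (B against A). The second is "To evaluate the efficacy and safety of Ningmitai Capsules combination with Silodosin Capsules versus Silodosin Capsules alone" (C against B). Here A is tamsulosin + placebo, B is silodosin + placebo and C is silodosin + Ningmitai.

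On visits, SAP 2(3)② says: "The changes of IPSS scores, IPSS sub-scores and QoL scores were compared between groups at 1, 2, 4, 8 and 12 weeks after treatment". That sentence names no test. The endpoint list in the Protocol, repeated in the SAP document, gives secondary IPSS total at weeks 1, 2, 4 and 8, and QoL at weeks 4, 8 and 12. IPSS total at week 12 is the primary endpoint.

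**The concern.** Each of these four endpoints is a change from baseline, so the baseline value is already in the data set. Using it only by subtraction fixes its coefficient at 1. ANCOVA estimates that coefficient and in large samples is never less precise. The choice costs precision on the secondary contrasts, with no saving in data or conduct.

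The second issue is specification. One-way ANOVA produces an F test across three arms, whereas the objectives need B−A and C−B. The level 0.0167 points to pairwise tests, but the ANOVA route does not say which test, which contrasts, or whether 0.0167 applies to the F test or to the pairs. These matters would be settled later, possibly after unblinding.

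The third issue is small: the SAP text and the endpoint list disagree on which visits are compared, so it is unclear whether QoL at weeks 1 and 2 is an endpoint or a description.

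**Working it through.** **The plan's own figure.** 0.05/3 = 0.01667, which rounds to the stated 0.0167. Divisors 2 and 4 give 0.025 and 0.0125. Three arms form three pairs (B−A, C−B, C−A), so the level fits pairwise testing. The matching CI level is 1 − 0.05/3 = 98.33%.

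**Within-endpoint error.** The Bonferroni bound for three pairs is 3 × 0.01667 = 0.05. Three independent tests would give 1 − (1 − 0.01667)³ = 0.049. Simulation with shared arms, no true differences and three pairs at this level gave 0.044 for normal means. It also gave 0.044 for ANCOVA with 83 per arm and correlation 0.5. (83 is 312/3 = 104 per arm, times 0.8 for the 20% dropout.) Error control within an endpoint is therefore sound with or without the covariate.

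**Precision.** Let σ be the baseline SD, kσ the follow-up SD, ρ the correlation between them and n the number per arm. The documents give none of σ, k or ρ, so k and ρ are assumed over a range. In large samples the variance of a contrast between two arms is:

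- change score: (2/n)σ²(1 + k² − 2ρk)
- ANCOVA on baseline: (2/n)σ²k²(1 − ρ²)

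The ratio ANCOVA/change is k²(1 − ρ²)/(1 + k² − 2ρk). The difference, change minus ANCOVA, is (2/n)σ²(1 − ρk)². It cannot be negative, and it is zero only where ρk = 1.

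With k = 1 the ratio simplifies to (1 + ρ)/2; at ρ = 0.5 it is 0.75. Ratios, with the variance cut in brackets:

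| k | ρ = 0.3 | ρ = 0.5 | ρ = 0.7 | ρ = 0.9 |
|---|---|---|---|---|
| 0.8 | 0.502 (50%) | 0.571 (43%) | 0.628 (37%) | 0.608 (39%) |
| 1 | 0.65 (35%) | 0.75 (25%) | 0.85 (15%) | 0.95 (5%) |
| 1.25 | 0.784 (22%) | 0.893 (11%) | 0.981 (2%) | 0.950 (5%) |

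At k = 1.25 and ρ = 0.8, ρk = 1 and the cut is zero: 1.5625 × 0.36 / (2.5625 − 2) = 0.5625/0.5625 = 1.

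At k = 1 the cuts are equivalent to 1/0.65 = 1.54, 1/0.75 = 1.33, 1/0.85 = 1.18 and 1/0.95 = 1.05 times as many patients.

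**Visits.**

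| Score | SAP 2(3)② | Secondary endpoint list | Extra in SAP |
|---|---|---|---|
| IPSS total | 1, 2, 4, 8, 12 | 1, 2, 4, 8 | week 12 (the primary endpoint) |
| Two IPSS sub-scores | 1, 2, 4, 8, 12 | 1, 2, 4, 8, 12 | none |
| QoL | 1, 2, 4, 8, 12 | 4, 8, 12 | weeks 1 and 2 |

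Counting the sub-scores separately, the SAP has 4 × 5 = 20 endpoint-visits and the list 4 + 2 × 5 + 3 = 17. This assumes that the obstruction score shares the weeks printed with the stimulation score in the same list item. Counted as one item, the sub-scores give 15 against 12, and the gap is still 3. Only the two QoL visits appear nowhere in the endpoint list.

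**The case against.** The strongest reply is that ANCOVA is here an efficiency choice. Under randomisation an unadjusted comparison of changes is valid and unbiased. That stands, and the point claims nothing more than lost precision.

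The gain may also be modest. Eligibility truncates baseline Qmax (4 to 15 ml/s), PVR (at most 100 ml) and prostate volume (at least 30 ml). A follow-up SD above the baseline SD is therefore plausible for Qmax and PVR, though this is inference. At k = 1.25 the cut is at most 22% over the correlations shown. For a stable measure such as prostate volume, ρ near 0.9 with equal SDs gives 5%. Nor does the gain carry over to the rank-sum route. All this limits the size of the benefit but gives no reason to prefer the unadjusted ANOVA.

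Two stronger readings are tempting, and the documents support neither:

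- A reader might infer that the analysis ends at the F test, so that a difference confined to tamsulosin could be taken as evidence about adding Ningmitai. No section says so. The very next sentence sets 0.05/3, a division that a lone F test would not need, and the rank-sum test offered as the alternative compares two groups. The pairwise comparisons are implied; what is missing is their specification.
- A reader might infer that the primary endpoint is tested a second time by the secondary rules. That follows only from reading the visit sentence literally. SAP 2(1) already places week-12 IPSS total for B against A under a one-sided 0.025 non-inferiority test. It does the same for superiority of C over B ("Ningmitai + Silodosin group and Silodosin + placebo group were compared by superior test").

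**Conclusion.** The point holds as an avoidable loss of precision plus an incomplete specification. The size depends on quantities the documents do not give. With equal SDs, the variance cut is 35% to 5% for correlations of 0.3 to 0.9. With a follow-up SD 0.8 to 1.25 times the baseline SD, it runs from about 50% down to zero, and in large samples it is never negative. The unnamed pairwise procedure is a gap in wording, since 0.0167 already implies three pairs. The visit mismatch is minor. Neither the primary conclusion nor the error rate within a secondary endpoint is affected.

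**What to change.** - For the continuous secondary endpoints, replace ANOVA on change scores with ANCOVA including the baseline value of the same measure. This also supplies a method for the IPSS and QoL comparisons, for which the visit sentence names none.
- Name the pairs B−A, C−B and C−A, each tested at two-sided 0.0167 and reported with a 98.3% CI.
- Keep the pairwise rank-sum test at the same level as the alternative the SAP already allows, with the choice made endpoint by endpoint before unblinding.
- Limit the visit sentence to IPSS total at weeks 1, 2, 4 and 8, the sub-scores at weeks 1, 2, 4, 8 and 12, and QoL at weeks 4, 8 and 12. Alternatively, label QoL at weeks 1 and 2 descriptive.
- State that week-12 IPSS total for B against A and C against B is tested only under SAP 2(3)①, and say what status C against A has at that visit.

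The cost is SAP wording, one model degree of freedom, the assumption of a roughly linear relation with baseline, and slightly more analysis work. Conduct, data collection and sample size do not change.
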